6.2 DURATION OF STUDY PARTICIPATION

6.2.1 Duration of study participation for each patient

The maximum study duration per patient will be approximately 224 weeks (4.3 years, patients from Part 2 only) to 272 weeks (5.5 years, patients from Part 1 enrolling in Part 2), or to 288 weeks for Japanese patients (5.9 years, Japanese patients from Part 1 enrolling in Part 2).

Part 1: Dose escalation phase

The maximum study duration per patient will be approximately 50 weeks (or 66 weeks for Japanese patients), inclusive of the screening period. Three sequential cohorts are planned. Patients will receive either placebo or GZ/SAR402671 (4 mg, 8 mg, or 15 mg) for a minimum 8 weeks per cohort (and maximum of 36 weeks [or 52 weeks for Japanese patients], for Cohort 1).

Safety/tolerability data will be analyzed at the end of 4 weeks of treatment at each cohort before proceeding to the next cohort.

Part 2: Treatment phase

The total study treatment duration (Periods 2 and 3) is approximately 208 weeks (4 years).

The study comprises 4 main periods:

- Period 1: the up to 60-day screening period.
- Period 2: the 52-week double-blinded, randomized treatment period.
- Period 3: the 156-week LTFU period during which eligible patients will all receive GZ/SAR402671.
- Period 4: the 8-week post-treatment observation period with end of study visit.

Therefore, maximum duration for a patient will be approximately 224 weeks.

6.2.2 Determination of end of clinical trial (all patients)

The end of the study is defined as being the “last patient last visit” planned with the protocol, including the follow-up visit (Visit 9 in Part 1 and Visit 16 in Part 2 or Visit 15 for patients who will transition to a long-term study with GZ/SAR402671). The Sponsor reserves the right to discontinue the study at any time.

6.3 INTERIM ANALYSIS

No interim analysis is planned for this study.

6.4 STUDY COMMITTEES

6.4.1 Data monitoring committee

A DMC, operating independently from the Sponsor and Clinical Investigators, will be responsible for overseeing the safety of patients and the risk/benefit ratio throughout the study. This committee is composed of externally based individuals with expertise in the disease under study, biostatistics, and/or clinical research. The primary responsibilities of the DMC are to ensure the patients welfare as well as to evaluate and review the safety and other applicable data throughout the course of the study and make appropriate recommendations to the Sponsor regarding the conduct of the clinical trial. The specific responsibilities of the DMC will be described in the DMC Charter.

6.4.2 Scientific advisory committee

The Scientific Advisory Committee (SAC) is composed of field experts and Sponsor-based scientists with clinical and methodological expertise. This Committee, led by a Chairperson, selected by the Sponsor, will provide advice to the Sponsor regarding scientific issues and operational conduct of the study. The SAC will also review any amendments, and provide input

regarding interpretation of study results. The members will remain blinded until completion of the study.

Among its responsibilities, the SAC will receive blinded study status reports from the Sponsor, and will review the recommendations from the DMC throughout the study.

Moreover, the SAC will also be responsible for the primary publication(s) emanating from the study. The Principal Investigator (PI) of the study will be selected by the Sponsor and will be the first author for the primary publication(s). Principal Investigators at the 3 first sites enrolling the most patients will also be included as authors for the primary publication, in addition to the other SAC members.

Detailed activities and responsibilities of the SAC are provided in the SAC charter.

6.5 DISCUSSION OF STUDY DESIGN

Current treatment options for PD patients, with or without GBA mutations, are limited due to side effects. Despite the many therapeutic agents available for the treatment of PD, patients can still experience intolerable disability due to disease progression. Thus, there is a high unmet medical need for better treatment alternatives in PD. Participation in this placebo-controlled study, with a novel mechanism of action, would present a unique opportunity for the patients. Patients will be allowed to start on PD therapy (only an immediate release levodopa formulation is allowed) or to continue to take their medication as usual (if already taking PD medication at study start).

Of note, PD prescription medications permitted (see [Section 8.8](#)) in this trial include:

- Dopamine replacement therapies (eg; levodopa/carbidopa).
- Dopamine agonists (eg; pramipexole, ropinirole, bromocriptine).
- Monoamine oxidase B inhibitors (eg; rasagiline).
- Catechol-O-methyltransferase inhibitors (eg; entacapone, tolcapone).
- Anticholinergics (eg; artane, cogentin).

The following points were taken into consideration in the design of the study:

- **Screening:** Sequencing of the GBA gene and genotyping for a LRRK2 (G2019S) mutation to ensure patient eligibility will be conducted from a collected whole blood sample even if historical results are available.
- **Randomization (Day 1, pre-dose):** To reduce the risk of imbalance between treatment groups with respect to cognitive function and PD medication. In Part 2, randomization will be stratified based on use of levodopa/PD medication (yes/no), cognitive function (MoCA score <26 [yes/no]) and severe GBA mutation (yes/no).
- **Long-term follow-up (Part 2):** Upon completion of the 52-week treatment period, eligible patients will be followed in an LTFU period for 36 months. Patients in the placebo arm will be switched to GZ/SAR402671 treatment after completing the Week 52 study visit. During the LTFU period, study drug assignment will remain blinded and patients will continue to be assessed by a blinded rater, thus collecting important information and

data. This will allow not only the long-term safety to be assessed but can also support long-term efficacy of GZ/SAR402671. Importantly, patients who received placebo in Period 2 will have the opportunity to receive GZ/SAR402671 treatment. Analysis of efficacy and safety between those patients who were on GZ/SAR402671 treatment from the start of randomization and patients who began GZ/SAR402671 treatment 1 year later will potentially offer insightful information on delayed start of treatment in this patient population.

- **Primary and secondary efficacy endpoints:** The primary efficacy endpoint of the study is the change from baseline to Week 52 in the Movement Disorder Society-Unified Parkinson's Disease Rating Scale (MDS-UPDRS), PART II+III. The MDS-UPDRS was designed to be more comprehensive than the original UPDRS, with new items devoted to several nonmotor elements of PD, including cognitive function. Based on a published critique of the UPDRS, the 5-point range for each item was retained, and clinical anchors of normal (0), slight (1), mild (2), moderate (3), and severe (4) were added to provide a consistency across items. Importantly, the MDS-UPDRS places greater emphasis on distinguishing relatively mild impairments and disabilities, drawing distinctions between slight and mild, whereas former distinctions between severe and marked are now collapsed into the severe rating. The incorporation of 'slight' and 'moderate' ratings in the scale should result in an even more sensitive measure of disease progression in early stages. The subscales are now titled: (Part I) nonmotor experiences of daily living (13 items), (Part II) motor experiences of daily living (13 items), (Part III) motor examination (18 items), and (Part IV) motor complications (6 items).

An important addition to the MDS-UPDRS is a set of detailed instructions. These are officially part of the scale, so that international colleagues can perform ratings in a systematic manner within and across centers. The instructions are intended to standardize the method of application of the scale so that the MDS-UPDRS data are collected uniformly. The MDS-UPDRS tool includes clear definitions of 'ON' times, when dopaminergic medications are working properly, and 'OFF' times, when the dopaminergic therapies 'wear off', and patients experience decreased mobility, to ensure uniformity of rater assessments of ON/OFF status (Note: PD medication cannot be taken for at least 12 hours prior to the visits including efficacy assessment). The scale has been translated in many different languages, and, importantly, scale reliability, construct validity, and precision have been assessed. It performs extremely well in comparison with the original version with high internal consistency for the entire scale as well as high internal consistency on each part. In addition, even though restructured, each part of the MDS-UPDRS correlates highly with the corresponding part of the original scale.

In summary, the MDS-UPDRS is a reliable and sensitive measure of disease progression, particularly decline in motor function, in early stages of PD. Given the target population for this study is early-stage GBA-PD patients, the change in the motor parts of the MDS-UPDRS (PART II+III) is the most appropriate scale to use as a primary endpoint in this clinical trial.

GBA-PD patients also experience more rapid cognitive decline as compared with PD patients without GBA mutations. Cognition changes in GBA-PD patients will be captured via assessment of the Parkinson's Disease-Cognitive Rating Scale (PD-CRS), a scale that was designed to cover

the full spectrum of cognitive deficits associated with PD. This secondary endpoint will allow important data to be gathered in this patient population.

Given that GBA-PD patients experience nonmotor symptoms, another important secondary endpoint will be the MDS-UPDRS, PARTS I+II+III. Lastly, functional scales are important for assessment in clinical trials, allowing to support clinical meaningfulness of endpoints. The H&Y score has been shown to have moderate correlations with Parts I and IV, and high correlations with Parts II and III of the MDS-UPDRS.

- **Pharmacodynamic and exploratory biomarkers:** GBA-mutations and reduced GCase activity can lead to elevations in plasma and CSF concentrations of substrates including GL-1 and lyso-GL-1. GZ/SAR402671 has shown to reduce plasma concentrations even in normal healthy volunteers in the repeated-dose Phase 1 study (Study TDR12768). Plasma and CSF samples will be stored and will be used to assess changes in GL-1 and lyso-GL-1 to support the clinical endpoints. Glucocerebrosidase activity will be explored. In addition, biomarkers associated with PD and/or neurodegeneration may also be assessed in blood and/or CSF, such as total α -Syn, NFL, tau, phospho-tau, as well as beta-amyloid (1-40, and 1-42).
- **Imaging:** PD, including GBA-PD, has been associated with changes in dopamine transport density in the basal ganglia regions in the brain, as measured by ioflupane-I-123 injection DATSCAN™ (from now on referred to as DAT scan). Changes in DAT scans in predefined areas of interest, such as the caudate nucleus, from baseline to Week 52 and from baseline to Week 104, Week 156, and week 208 will be assessed as an exploratory endpoint. Please note that DAT scans will be performed only in countries where it is approved.

7 SELECTION OF PATIENTS

7.1 INCLUSION CRITERIA

I 01. Male or female subjects with a diagnosis of PD (with at least two of the following signs: resting tremor, postural instability, akinesia/hypokinesia, and muscle rigidity) and who are heterozygous carriers of a GBA mutation. Please see [Section 17 \(Appendix A\)](#) for the list of most common mutations. Note: If the patient has a GBA mutation that is not on the list, a consult will always be required to determine the eligibility of the patient.

OR

I 02. Patients carrying known sequence variants associated with GBA-PD ([Section 17 \[Appendix A\]](#)), in addition to having a diagnosis of PD (with at least 2 of the following signs: resting tremor, postural instability, akinesia/hypokinesia or muscle rigidity), must also have a diagnosis of rapid eye movement sleep behavior disorder (RBD) (15) confirmed by historically documented polysomnography or by RBD screening questionnaire (see [Section 17 \[Appendix B\]](#)).

I 03. Age ≥ 18 years to 80 years, inclusive, at the time of signing the informed consent (FOR JAPANESE PATIENTS ONLY: Age ≥ 20 years to 80 years, inclusive, at the time of signing the informed consent. Note: Japanese patients refers only to Japanese patients enrolled and living in Japan [[Appendix T](#)]).

I 04. Has symptoms of PD for ≥ 2 years.

I 05. Hoehn and Yahr stage of ≤ 2 for PD at baseline; for patients on a stable dose of PD medication, this should be done in the "ON" state.

I 06. If on levodopa or any other PD medication (such as a dopamine agonist), the medication regimen must be stable for at least 30 days (at least 60 days for rasagiline) prior to randomization.

I 07. Cooperative, able to ingest oral medication, and able to complete all aspects of the study and capable of doing so, alone, according to the Investigator's judgment.

I 08. The patient is willing to abstain from consumption of grapefruit, grapefruit juice, and/or grapefruit containing products for 72 hours prior to administration of the first dose of GZ/SAR402671 and for the duration of the entire treatment period (Part 1 and Part 2, Periods 2 and 3).

I 09. Able to provide a signed written informed consent.

7.2 EXCLUSION CRITERIA

Patients who have met all the inclusion criteria listed in [Section 7.1](#) will be screened for the following exclusion criteria which are sorted and numbered in the following subsections.

7.2.1 Exclusion criteria related to study methodology

- E 01. Parkinsonism due to drug(s) and/or toxin(s).
- E 02. Patients carrying the LRRK2 G2019S mutation.
- E 03. Patients with GD as defined by clinical signs and symptoms (ie, hepatosplenomegaly, cytopenia, skeletal disease) and/or marked deficiency of GCase activity compatible with GD.
- E 04. MoCA score of <20.
- E 05. Patients who have past surgical history of deep brain stimulation.
- E 06. Patients who have a baseline MRI without contrast showing a structural abnormality that is a possible etiology of PD related signs and symptoms.
- E 07. Any medical disorders and/or clinically relevant findings in the physical examination, medical history, or laboratory assessments that, in the opinion of the Investigator, could interfere with study-related procedures (eg, heart failure, hypokalemia, etc). This includes condition(s) that precludes the safe performance of routine LP, such as prohibitive lumbar spinal disease, bleeding diathesis, or clinically significant coagulopathy or thrombocytopenia.
- E 08. Current participation in another investigational interventional study.
- E 09. Current treatment with anticoagulants (eg, coumadin, heparin) that might preclude safe completion of the LP.
- E 10. An investigational medicinal product (IMP), including ambroxol, within 3 months or 5 half-lives, whichever is longer, before study inclusion.
- E 11. Presence of severe depression as measured by Beck Depression Inventory, second edition (BDI-II) >28 and/or a history of a major affective disorder within 1 year of screening examination.
- E 12. A history of drug and/or alcohol abuse within the past year prior to the first screening visit.
- E 13. A known hypersensitivity to DAT scan (either the active substance of ioflupane I-123 or to any of the excipients).

- E 14. The patient is sexually active and is not willing to use 2 forms of birth control during the study and up to 90 days after the day of last dose (see contraceptive guidance in [Section 17 \[Appendix C\]](#)).
- Women of childbearing potential (WOCBP) not protected by 2 highly effective methods of birth control and/or who are unwilling or unable to be tested for pregnancy for up to 45 days after the day of last dose.
 - Male participants must use 2 forms of birth control during the study and refrain from donating sperm up to 90 days after the day of last dose. If the patient has a female partner of childbearing potential, the patient must wear a condom and female partner must use at least 1 highly effective methods of birth control.
- E 15. The patient is scheduled for in-patient hospitalization including elective surgery during the study.
- E 16. The patient, in the opinion of the Investigator, is unable to adhere to the requirements of the study. This includes any patient who, in the judgment of the Investigator, is likely to be noncompliant during the study, or unable to cooperate because of a language problem or poor mental development.
- E 17. Any country-related specific regulation that would prevent the subject from entering the study.
- E 18. Any patient who is the Investigator or any Sub-Investigator, research assistant, pharmacist, study coordinator, other staff or relative thereof directly involved in the conduct of the study.
- E 19. Know hypersensitivity to GZ/SAR402671 or any component of the excipients.

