1.3.3 Part 2: Study schedule of assessments (Periods 3 and 4)

Study Period	Long-Term Follow-up Period (Period 3)												8-Week Follow-up Visit (Period 4)
	W65 ^f (±7 days)	W78 ^f (±7 days)	W91 ^f (±7 days)	W104 (2 years) ^f (±7 days)	W117 ^f (±7 days)	W130 ^f (±7 days)	W143 ^f (±7 days)	W156 ^f (3 years) (±7 days)	W169 ^f (±7 days)	W182 ^f (±7 days)	W195 ^f (±7 days)	W208 ^f (4 years) (±7 days)	
Visit number	9.1 (for Japanese patients only)	10	10.1 (for Japanese patients only)	11	11.1 (for Japanese patients only)	12	12.1 (for Japanese patients only)	13	13.1 (for Japanese patients only)	14	14.1 (for Japanese patients only)	15	16
Visit at clinical site	X	X	X	X	X	X	X	X	X	X	X	X	X
Concomitant medications	X	X	X	X	X	X	X	X	X	X	X	X	X
Study treatment administration													
GZ/SAR402671	qd												
Dispense IMP		X		X		X		X		X			
Dispense/check patient diary		X		X		X		X		X		X ^b	X ^b
Biomarkers^c													
Biomarkers: serum and plasma				X				X				X	
Safety													
Physical examination				X				X				X	X

Study Period	Long-Term Follow-up Period (Period 3)												8-Week Follow-up Visit (Period 4)
	W65 ^f (±7 days)	W78 ^f (±7 days)	W91 ^f (±7 days)	W104 (2 years) ^f (±7 days)	W117 ^f (±7 days)	W130 ^f (±7 days)	W143 ^f (±7 days)	W156 ^f (3 years) (±7 days)	W169 ^f (±7 days)	W182 ^f (±7 days)	W195 ^f (±7 days)	W208 ^f (4 years) (±7 days)	
Visit number	9.1 (for Japanese patients only)	10	10.1 (for Japanese patients only)	11	11.1 (for Japanese patients only)	12	12.1 (for Japanese patients only)	13	13.1 (for Japanese patients only)	14	14.1 (for Japanese patients only)	15	16
Neurological examination		X		X		X		X		X		X	X
Vital signs, body temperature	X	X	X	X	X	X	X	X	X	X	X	X	X
Body weight				X				X				X	
Hematology				X				X				X	
Biochemistry, urinalysis				X				X				X	
Urine pregnancy test (for WOCBP)		X		X		X		X		X		X	
Ophthalmology examination ^d		X		X		X		X		X		X	X
12-lead ECG				X				X				X	
Adverse event collection	X	X	X	X	X	X	X	X	X	X	X	X	X
Assessments^e													
DAT scan				X				X				X	

Study Period	Long-Term Follow-up Period (Period 3)												8-Week Follow-up Visit (Period 4)
	Day (D) or Week (W) (allowed range)	W65 ^f (±7 days)	W78 ^f (±7 days)	W91 ^f (±7 days)	W104 (2 years) ^f (±7 days)	W117 ^f (±7 days)	W130 ^f (±7 days)	W143 ^f (±7 days)	W156 ^f (3 years) (±7 days)	W169 ^f (±7 days)	W182 ^f (±7 days)	W195 ^f (±7 days)	

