Visit number	9.1 (for Japanese patients only)	10	10.1 (for Japanese patients only)	11	11.1 (for Japanese patients only)	12	12.1 (for Japanese patients only)	13	13.1 (for Japanese patients only)	14	14.1 (for Japanese patients only)	15	16
MDS-UPDRS (including H&Y)		X		X		X		X		X		X	X
PD-CRS		X		X		X		X		X		X	
MoCA		X		X		X		X		X		X	
SDMT (oral)		X		X		X		X		X		X	
TMT-A; TMT-B		X		X		X		X		X		X	
BDI-II		X		X		X		X		X		X	X
PDQ-39		X		X		X		X		X		X	
EQ-5D		X		X		X		X		X		X	
FES		X		X		X		X		X		X	
HRPQ		X		X		X		X		X		X	

Abbreviations: AE, adverse event; BDI-II: Beck Depression Inventory, second edition; CGI: Clinical Global Impression; DAT: dopamine transporters; DAT scan, ioflupane I-123 injection DaTSCAN; ECG: electrocardiogram; EQ-5D: EuroQol Five Dimensions questionnaire; FES: Falls Efficacy Scale; GL-1: glucosylceramide; H&Y: Hoehn and Yahr; HRPQ: Health-Related Productivity questionnaire; IMP, investigational medicinal product; lyso-GL-1: glucosylsphingosine; MDS-UPDRS: Movement Disorder Society-Unified Parkinson's Disease Rating Scale; MoCA: Montreal Cognitive Assessment; PD: Parkinson's disease; PD-CRS: Parkinson's Disease-Cognitive Rating Scale; PDQ-39: Parkinson's Disease Questionnaire – 39; qd, daily; SDMT: Symbol Digit Modalities Test; TMT-A: Trail-Making Test A; TMT-B: Trail Making Test B; WOCBP: women of childbearing potential.

- a* This is the study completion visit, and it should be done 8 weeks after last IMP dose; this visit also applies to early withdrawal or treatment discontinuation, if applicable. This does not apply to patients who will transition to a long-term study with GZ/SAR402671 (last visit will be week 208).
- b* Retrieve patient diary. For patients transitioning to a long-term study with GZ/SAR402671 the patient diary will be retrieved at week 208.
- c* Plasma biomarkers, including plasma GL-1 and lyso-GL-1.
- d* After 52 weeks, the patient is required to have a full ophthalmological examination at Weeks 104, 156, 208, and early withdrawal or treatment discontinuation, if applicable. Visual acuity check, slit lamp examination and funduscopy without pupil dilation are only required at Weeks 78, 130, 182, and 216 (at the 8-week follow-up [Period 4] visit). Pupil dilation/full evaluation can be performed at any time if deemed medically necessary.

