10.1.1.9 Visit 9: Safety follow-up completion visit (± 3 days)

The Part 1 safety follow-up completion visit (Visit 9) should be done approximately 6 weeks after last IMP dose; this visit also applies to early withdrawal or permanent treatment discontinuation, if applicable.

The following assessments will be performed as listed in the study flow chart, [Section 1.3.1](#), which should be done in the following order:

- BDI-II ([Appendix L](#))
- Review of concomitant medications
- Physical examination
- General neurological examination
- Visual acuity check, slit lamp examination, and fundoscopy without pupil dilation
- Vital signs: systolic and diastolic blood pressure (mm Hg), heart rate (bpm), respiratory rate (breaths/minute), and temperature ($^{\circ}\text{C}$)
- 12-lead ECG
- Laboratory assessments (to be performed by the central laboratory):
 - Hematology: CBC, with differential and platelet count; coagulation profile: PT, PTT, and INR
 - Biochemistry: Sodium, potassium, chloride, calcium, ALT, AST, GGT, ALP, total and conjugated bilirubin, urea, serum creatinine, glucose, albumin, total proteins
- Urinalysis (dipstick) including glucose, protein, bilirubin, urobilinogen, pH, specific gravity, blood, ketones, nitrite, and leucocytes. Central urinalysis will be performed if any abnormality is observed in the urinalysis dipstick test.
- Urine pregnancy test (for WOCBP)
- Review of current medical conditions, with AE/SAE reporting (if any)
- Retrieve patient diary

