10.1.2 Part 2: Treatment phase

In Part 2, the GZ/SAR402671 dose will be the highest dose determined to be safe and well tolerated in Part 1. If patients from Part 1 continue to meet eligibility requirements, they may enroll in Part 2, but rerandomization will be required. All assessment at baseline will need to be repeated, except for the genetic screening, MRI, LP, and DAT scan, to confirm eligibility of patients from Part 1 to enroll in Part 2 (see study flowchart, [Section 1.3.2](#)).

Visit window: The randomization visit (Day 1) can be performed within 60 days from the screening visit. For Week 2 through Week 39 visits, a time frame of ± 3 days is acceptable using Day 1 as reference. For Week 52, a visit window of ± 14 days is acceptable using Day 1 as a reference. After Week 52 and throughout Period 3, a visit window of ± 7 days for all visits is acceptable using Day 1 as reference. For Week 216, a visit window of ± 14 days is acceptable using Day 1 as a reference. (If one visit date is skipped/missed/changed, the next visit should take place according to the original schedule).

Covid-19 outbreak

Due to Covid-19 outbreak, on-site visits may be delayed with visit window extended up to 3 months. In this case, IMP can be dispensed to the patient (via direct-to-patient) for a maximum duration of 6 months without on-site visit, but with a follow-up by phone (see [Section 10.1.2.12](#)). If Week 52 visit is delayed, the blinded treatment will be continued until Week 52 visit is performed and eligibility assessed for LTFU period.

Prior to dispensing the IMP, the Investigator will contact (phone, on-line) the patient to review AE/SAE/concomitant medication to ensure that no safety issues contraindicate the prolongation of the IMP. During the time of IMP prolongation, the Investigator will make every effort to contact the patient every 2 weeks to assess the safety. All examinations required for safety that can't be done at the site can be performed locally at a minimum laboratory assessment.

The on-site visit should be scheduled as close as possible to the theoretical visit date, particularly Week 52 which is mandatory.

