10.1.2.10 Long term follow-up period (Period 3)

Patients who complete the 52 weeks of double-blinded treatment and who continue to meet inclusion criteria [I 06](#), [I 07](#), [I 08](#), and [I 09](#) and none of the exclusion criteria (exclusion criteria [E 02](#), [E 03](#), [E 05](#), and [E 06](#) will not need to be rechecked) will be eligible to enroll to the LTFU period (Period 3) where they will continue to receive appropriate monitoring and will receive GZ/SAR402671 treatment after Visit 9. It is important to note that patients will not be informed of when the switch will occur, nor will the person(s) performing any of the evaluations.

Throughout Period 3, a visit window of ± 7 days for all visits is acceptable using Day 1 as reference.

During this period, a clinic visit will be scheduled at 6-month intervals (Weeks 78, 104, 130, 156, 182, and 208) and patients will receive GZ/SAR402671, orally, at the clinic. For Japanese patients only, additional clinic visit will be scheduled at Weeks 65, 91, 117, 143, 169, and 195 (Visits 9.1, 10.1, 11.1, 12.1, 13.1, and 14.1) in addition to the above 6-month interval visits.

Before dosing, the following assessments will be performed at each study visit (every 6 months), as listed in the study flow chart, [Section 1.3.3](#), which should be done in the following order:

- Whenever possible, the following scales and questionnaires should be done prior to clinical interaction with the Investigator:
 - BDI-II ([Appendix L](#))
 - PDQ-39 ([Appendix O](#))
 - EQ-5D ([Appendix P](#))
 - HRPQ ([Appendix R](#))
 - FES ([Appendix Q](#))
- MDS-UPDRS, including H&Y ([Appendix F](#))
- PD-CRS ([Appendix G](#))
- Other questionnaires and scales
 - MoCA ([Appendix I](#))

- Oral SDMT ([Appendix J](#))
- TMT-A; TMT-B ([Appendix K](#))
- Review of concomitant medications (every 3 months [13 weeks] for Japanese patients only)
- General neurological examination
- Visual acuity check, slit lamp examination, and fundoscopy without pupil dilation at Visits 10, 12, and 14; at Visits 11, 13, and 15, patients will have a full ophthalmology examination and photography (must be performed after the neurological examination)
- Vital signs: systolic and diastolic blood pressure (mm Hg), heart rate (bpm), respiratory rate (breaths/minute), and temperature (°C) (every 3 months [13 weeks] for Japanese patients only)
- Urine pregnancy test (for WOCBP)

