- Review of current medical conditions, with AE/SAE reporting (if any) (every 3 months [13 weeks] for Japanese patients only)
- Dispense IMP

At Visit 11/Week 104, Visit 13/Week 156, and Visit 15/Week 208 (ie, yearly), the following additional assessments will be performed, as listed in the study flow chart, [Section 1.3.3](#):

- Blood sampling for biomarker analysis
- Physical examination and record of body weight measurement
- 12-lead ECG
- Laboratory assessments (to be performed by the central laboratory):
 - Hematology: CBC, with differential and platelet count; coagulation profile: PT, PTT, and INR
 - Biochemistry: Sodium, potassium, chloride, calcium, ALT, AST, GGT, ALP, total and conjugated bilirubin, urea, serum creatinine, glucose, albumin, total proteins
- Urinalysis (dipstick) including glucose, protein, bilirubin, urobilinogen, pH, specific gravity, blood, ketones, nitrite, and leucocytes. Central urinalysis will be performed if any abnormality is observed in the urinalysis dipstick test.
- DAT scan
- Dispense IMP (except Visit 15/Week 208)
- Retrieve patient diary (at Visit 15/Week 208, only for patients who will transition to a long-term study with GZ/SAR402671).

Remind patient to return to the clinic for next visit.

Remind patient to not take the dose at home on the clinic visiting day, the IMP will be taken at clinic.

At Visit 15 (Week 208), patients will receive their last dose of GZ/SAR402671 at the clinic.

Visit 15 (Week 208) will be the last study visit for patients who will transition to a long-term study with GZ/SAR402671.

10.1.2.11 Eight-week follow-up visit (Period 4, end-of-study visit, Visit 16: Week 216 ±14 days)

This will be the last study visit. Patients who prematurely and permanently discontinue study medication should complete an end of treatment assessment visit (similar to Week 52/end of treatment visit for Period 2, Part 2) followed by a 8-week post-treatment follow-up visit (Visit 16). The following assessments will be performed as listed in the study flow chart, [Section 1.3.3](#), which should be done in the following order:

- BDI-II (Appendix L)
- MDS-UPDRS, including H&Y ([Appendix F](#))
- Review of concomitant medications
- Physical examination
- General neurological examination
- Visual acuity check, slit lamp examination, and fundoscopy without pupil dilation
- Vital signs: systolic and diastolic blood pressure (mm Hg), heart rate (bpm), respiratory rate (breaths/minute), and temperature (°C)

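### The closing visit for patients who stop treatment in Period 3 is defined in two ways, with two smaller gaps: no post-dose pregnancy test for Part 2 completers, and 1 versus 2 contraceptive methods for women on HRT of doubtful menopausal status

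*Protocol*

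**What the plan says.** **Closing visit after stopping in Period 3.** The assessment schedule in the synopsis asks patients who stop early for an end-of-treatment visit of the Week 52/Visit 9 kind, for Period 2 and Period 3 alike, and then a follow-up visit of the Visit 16 kind. Section 10.1.2.11 also refers to the Week 52 visit. Sections 10.3.3 and 10.3.4 send patients who stop in Period 3 to Week 216 procedures instead, and 10.3.4 then adds the Visit 16 follow-up. Section 10.3.5 repeats the Week 216 rule for withdrawal from the study. Footnote d of 1.3.3 and section 9.3.3.6 require a full ophthalmological examination at treatment discontinuation.

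**Pregnancy testing after the last dose.** E 14, in 7.2.1 and in the synopsis, excludes women of childbearing potential who are "unwilling or unable to be tested for pregnancy for up to 45 days after the day of last dose". In Part 1 the urine test is on the list for the closing visit: "The Part 1 safety follow-up completion visit (Visit 9) should be done approximately 6 weeks after last IMP dose". In Part 2 the pregnancy-test row of 1.3.3 is marked at Visits 10 to 15 and blank at Visit 16, and the Visit 16 list in 10.1.2.11 has no test. Assessments at Week 208 come before dosing (10.1.2.10), and "At Visit 15 (Week 208), patients will receive their last dose of GZ/SAR402671 at the clinic". On Visit 16, footnote a of 1.3.3 says: "This is the study completion visit, and it should be done 8 weeks after last IMP dose".

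**Contraception.** E 14 excludes "Women of childbearing potential (WOCBP) not protected by 2 highly effective methods of birth control". Appendix C asks women on HRT whose menopausal status is in doubt for one highly effective method if they stay on HRT. It also counts a woman as of childbearing potential until she is postmenopausal or permanently sterile.

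**The concern.** A site closing out a patient who stops in Period 3 cannot follow both definitions of the visit, and they differ in most safety content. Lens opacities, ALT increase and pregnancy are all adverse events of special interest (10.4.1.3). The Week 216 version has no laboratory tests and no pregnancy test, and its eye examination is the limited one without pupil dilation. If sites choose differently, closing safety data in Period 3 will be unevenly collected.

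For pregnancy, women are asked at entry to accept testing after the last dose, but the Part 2 schedule makes no use of that acceptance for those who complete treatment. A test taken just before the final dose cannot show a later conception and may miss a very recent one. Pregnancies have to be followed to outcome, so one closing test would help to find them.

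The HRT sentence gives one small group of women two different contraceptive requirements.

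**Working it through.** **1. Content of the two closing visits**

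| Assessment | Week 52 type (10.1.2.9) | Week 216 type (10.1.2.11, 1.3.3) |
|---|---|---|
| Hematology, biochemistry, urinalysis | yes | no |
| 12-lead ECG | yes | no |
| Urine pregnancy test | yes | no |
| Eye examination | full, with photography | limited, no dilation |
| LP, DAT scan, PK | yes | no |
| Physical and neurological examination, vital signs, AEs, MDS-UPDRS, BDI-II | yes | yes |

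Under 10.3.4 the sequence after stopping in Period 3 is the right-hand column, followed eight weeks later by Visit 16, which is the right-hand column again.

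Period 3 laboratory tests and ECGs are at Weeks 104, 156 and 208, so consecutive ones are 156 − 104 = 52 weeks apart. A patient who stops just before one of these visits, has a Week 216-type closing visit and declines further scheduled visits could therefore leave with the last scheduled laboratory tests and ECG almost 52 weeks old. Pregnancy tests are 26 weeks apart.

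**2. Scheduled pregnancy tests**

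- Part 2 completers: 6 in Period 3 (Weeks 78, 104, 130, 156, 182 and 208), all pre-dose, and 0 after the last dose.
- Part 1: 1 after the last dose, at Visit 9. 6 × 7 = 42 days, and 42 ± 3 gives days 39 to 45, which fits the 45-day limit in E 14.
- Patients stopping in Period 3: 1 at the closing visit under the synopsis, 0 under 10.3.3 and 10.3.4. The follow-up visit has none under either.

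**3. Where a Visit 16 test would fall**

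- Nominal: (216 − 208) × 7 = 56 days after the last dose, which is 56 − 45 = 11 days past the E 14 limit.
- Footnote a (8 weeks after the last dose) with the ±14-day window: 56 ± 14, so days 42 to 70. Only days 42 to 45 lie within the limit.
- Both windows referenced to Day 1, as in 10.1.2 (Week 208 ±7 days, Week 216 ±14 days): earliest 56 − 14 − 7 = 35, latest 56 + 14 + 7 = 77.

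These ranges are before any Covid-19 extension of visit windows by up to 3 months. On either reading, a test at Visit 16 would usually come after day 45, so the limit has to move with it. Both ranges stay inside the 90-day contraception period of E 14 (90 − 70 = 20 and 90 − 77 = 13 days to spare).

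**4. Contraceptive methods**

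- E 14, women of childbearing potential: 2 highly effective methods.
- Appendix C, women on HRT with doubtful status: 1.
- Appendix C, other women: acceptable methods listed, no number given.
- Appendix C, men: condom plus one further method, or abstinence. The condom-plus-one rule agrees with E 14.

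The conflict is confined to the HRT sentence.

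**The case against.** The strongest point concerns E 14. It is a criterion of willingness, and its 45 days is an outer limit, so a schedule without a post-dose test does not breach it. Unscheduled tests are not barred, and local law may require more. A reader might infer from the Part 1 schedule that Part 2 violates its own criterion; the text does not support that. What stands is that the Part 2 schedule never calls on the willingness it asks completers for.

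It can also be said that a Visit 16 test would usually miss the 45 days, so the remedy needs E 14 rewritten. That is correct, and the two changes belong together. Rewording E 14 has little effect at entry this late: it acts at entry and at the Week 52 recheck, and the Week 52 analysis was planned for early 2021. The operative changes are therefore those in the schedule and the discontinuation sections.

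On the closing visit, footnote a of 1.3.3 says that Visit 16 also applies after discontinuation, so Week 216 in 10.3.3 and 10.3.5 might simply mean the follow-up visit. Section 10.3.4 cannot be read that way, because it names both visits in sequence. The wording of 10.1.2.11 names Period 2, so for Period 3 the synopsis is the firmer source. A site that follows footnote d would do the full eye examination anyway; the laboratory tests, ECG and pregnancy test have no such backstop.

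On contraception, the HRT sentence stands under the postmenopausal heading and offers the alternative of stopping HRT to confirm status, so it can be read as a special rule. Appendix C's own definition nevertheless keeps these women within the group to which E 14 applies. A reader might infer that Appendix C asks only 1 method of all women of childbearing potential; it does not.

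**Conclusion.** The point holds as a set of minor safety inconsistencies. The most substantial is the double definition of the Period 3 closing visit: it concerns all patients who stop then, not only women, and reaches well beyond the pregnancy test. The missing post-dose test concerns Part 2 completers. The 1-versus-2 conflict concerns only women on HRT of doubtful menopausal status.

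Women who stop in Period 2 have a Week 52-type closing visit with a test under every section, and patients who stop but keep attending scheduled visits have the tests listed there. Patients moving to the long-term study end at Week 208 and have no Visit 16; that study's schedule is not at hand.

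The protocol does not give the number of women of childbearing potential or on HRT; I assume that it is small. The almost 52-week figure assumes that the patient declines further scheduled visits and that the site follows 10.3.3 and 10.3.4 literally. A reader should not infer any effect on the efficacy analysis: the primary endpoint is at Week 52, before Period 3 begins.

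**What to change.** 1. Align 10.3.3, 10.3.4 and 10.3.5 with the synopsis, so that the closing visit for patients who stop or withdraw in Period 3 is of the Week 52 kind. Keep the provision that the need to repeat LP, DAT scan and PK sampling is discussed with the Sponsor. Name Period 3 in 10.1.2.11.
2. Add a urine dipstick for women of childbearing potential at Visit 16 in 1.3.3 and 10.1.2.11. For Part 2, replace the 45-day limit in E 14 and in the synopsis with testing through Visit 16, which holds on either reading of the visit window.
3. In Appendix C, change the HRT sentence to 2 highly effective methods.

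The cost is one dipstick per woman at a visit that already takes place, a fuller closing visit for patients who stop in Period 3 wherever sites now use the Week 216 list, and wording changes in the sections named. The Visit 16 test does not reach patients who move to the long-term study.
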